7.3. Covariates

The analyses of the primary and secondary endpoints will be performed using the following randomization stratification factor as covariate:

- Age (<18, \geq 18 years of age)

Analyses of a given continue endpoint will also include its corresponding baseline as a covariate.

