9.2. Analyses of Primary Endpoint

Primary efficacy analysis will be based on the ITT population. The primary endpoint will be tested by Cochran Mantel Haenszel (CMH) test stratified by age. Common odds ratio and its 95% confidence interval will be provided. If the observed 2-sided p-value from the CMH test is

less than 0.05, statistical significance will be declared. Point estimates of the proportions for each treatment arm will be provided along with the corresponding 2-sided 95% confidence intervals. The point estimate of the difference of the proportions between treatment arms will also be provided along with corresponding 2-sided 95% confidence intervals.

For the above primary analysis, Patients who drop out of the study and patients who have unknown primary endpoint will be imputed as failures/non-responders, as stated in the handling of missing value section above.

As a sensitivity analysis, patients who drop out of the study and patients who have unknown primary endpoint will be imputed as responders. The primary analysis of CHM by age will be repeated.

One additional sensitivity analysis, the most conservative approach, will have following imputations:

- patients who drop out of the study and patients who have unknown primary endpoint in active arm will be imputed as failures/non-responders
- patients who drop out of the study and patients who have unknown primary endpoint in placebo arm will be imputed as responders

In addition, subgroup analyses by each age group (<18 , ≥ 18 years of age) will be conducted. For a given age group, unstratified CMH test will be performed. Furthermore, subgroup analyses by baseline nausea severity will also be conducted. None and mild severity will be combined as one group. For a given severity group, unstratified CMH test will be performed.

Primary analysis will also be performed on Subgroup Population 1 and Subgroup Population 2.

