9.3. Efficacy Analyses for Secondary and Tertiary Endpoints

ITT population will be used for the analyses of all secondary and tertiary endpoints.

1) Analyses of Binary/Proportion Endpoint

Same statistical test as for the analyses of the primary endpoint, as stated in Section 9.2, will be used for analyzing other proportion endpoints.

2) Analyses of Time-to-Event Endpoints

Time to event endpoints will be compared between the treatment arms using stratified log-rank test adjusting the age stratification factor. The endpoints will also be summarized using the Kaplan-Meier method and displayed graphically when appropriate. Median event times and 2-sided 95% confidence interval for each median will be provided.

3) Analyses of Continuous Endpoints

Descriptive statistics, including the mean, standard deviation, median, minimum, and maximum values, will be provided for continuous endpoints.

4) Analyses of Ordinal Categorical Endpoints

The number and percentage of patients in each category will be provided for categorical endpoints. Bristol Stool Scale (BSS), added in the Protocol Amendment 3, is an 8 point ordinal categorical variable. Wilcoxon rank sum test will be used to compare the two treatment groups.

5) Concordance Assessment of Bristol Stool Scale and Stool consistency

Stool consistency, as recorded per original protocol, none/formed (normal)/soft/watery (diarrhea), is a 4 point ordinal categorical variable. Cross-tabulation of stool consistency and BSS among all the patients who have both assessments at a given time point will be created to evaluate the concordance of the two scales. Cohen's Weighted Kappa Coefficient and 95% confidence interval will be provided.

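### SAP 7.3 commits secondary-endpoint analyses to the age stratum, but 9.3 item 4 names a Wilcoxon test with no stratum for the Bristol Stool Scale (minor)

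*SAP*

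**What the plan says.** Randomisation is stratified by age, under 18 against 18 and over (protocol 4.1 and 7.1; SAP 3.1). SAP 7.3 carries that into the analysis: "The analyses of the primary and secondary endpoints will be performed using the following randomization stratification factor as covariate", and the only factor it lists is age.

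The methods sections then name a test for each type of endpoint:

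- Primary endpoint (SAP 9.2): "The primary endpoint will be tested by Cochran Mantel Haenszel (CMH) test stratified by age".
- Other proportions (SAP 9.3 item 1): "Same statistical test as for the analyses of the primary endpoint, as stated in Section 9.2, will be used for analyzing other proportion endpoints".
- Times to event (SAP 9.3 item 2): "stratified log-rank test adjusting the age stratification factor".
- Ordinal endpoints (SAP 9.3 item 4), directly after the sentence that introduces the Bristol Stool Scale (BSS): "Wilcoxon rank sum test will be used to compare the two treatment groups".

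The BSS is listed as secondary in protocol 2.2, in the efficacy endpoints of the protocol synopsis, and in the secondary objectives of SAP 3.2.

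**The concern.** Item 4 is the only place in SAP 9.3 where a between-arm test is named without the age stratum. Nothing in 7.3 or 9.3 exempts ordinal endpoints. An analyst cannot satisfy both sections: the plain Wilcoxon test departs from 7.3, and a stratified test departs from the wording of 9.3 item 4. SAP section 3 requires deviations from the plan to be described in the study report, and here it is unclear which choice would be the deviation.

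There is also a modest statistical cost. Stratified randomisation balances age between the arms. If age is related to stool outcome, a test that ignores the stratum counts between-stratum spread as noise that the design has already removed. Its reference distribution is then slightly too wide. At stake are a little power and the consistency of one secondary comparison, not the trial's main conclusion.

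**Working it through.** **1. The rule against the methods.**

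| Endpoint type | Test named | Age stratum? |
|---|---|---|
| Primary | CMH | yes |
| Other proportions | same as primary | yes |
| Time to event | log-rank | yes |
| Ordinal (BSS) | Wilcoxon rank sum | not named |

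**2. The design figures used below.** Protocol 7.1 gives 40% against 20% failure, two-sided alpha 0.01, power 90%, allocation 60:40, and 192 + 128 = 320. With the pooled-variance formula and r = 1.5, the mean failure rate is (0.40 + 1.5×0.20)/2.5 = 0.28. Then n(placebo) = [2.576×√(0.28×0.72×(1+1/1.5)) + 1.282×√(0.24+0.16/1.5)]² / 0.20² = (1.493 + 0.755)²/0.04 ≈ 126.3, so 127. With 191 on active the total is 318. Power at 128/192 is 90.4%. The plan's 320 is reproduced.

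**3. How conservative the plain Wilcoxon test can be.** The share under 18 (w) and the age shift in within-stratum SD units (d) are assumptions, because the documents give neither. On a latent normal scale, total variance exceeds within-stratum variance by the factor 1 + w(1−w)d². A nominal 5% test then rejects under the null at about 2Φ(−1.96×√factor).

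- w = 0.30, d = 0.5: factor 1 + 0.21×0.25 = 1.0525, rejection about 4.4%.
- w = 0.30, d = 0.8: factor 1 + 0.21×0.64 = 1.134, rejection about 3.7%.
- d = 0: factor 1, rejection 5%.

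**4. Simulation of plain Wilcoxon against van Elteren.** Settings: an 8-category scale (SAP 9.3 calls the BSS an 8-point variable), 192 against 128 with 60:40 allocation inside each age stratum, an assumed treatment effect of 0.32 SD, two-sided 0.05, and 4,000 trials per setting.

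Null rejection by the plain Wilcoxon, %:

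| Age shift (SD) | 10% under 18 | 20% | 30% |
|---|---|---|---|
| 0 | 5.1 | 5.0 | 4.6 |
| 0.3 | 5.2 | 5.2 | 5.2 |
| 0.5 | 5.0 | 4.8 | 4.5 |
| 0.8 | 5.0 | 3.7 | 3.6 |

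Van Elteren rejects in 4.5–5.6% of trials over the same settings. The simulation standard error near 5% is √(0.05×0.95/4000) ≈ 0.34 points.

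Power gain of van Elteren over Wilcoxon, percentage points:

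| Age shift (SD) | 10% under 18 | 20% | 30% |
|---|---|---|---|
| 0 | 0.3 | 0.4 | 0.0 |
| 0.3 | 0.4 | 0.7 | 0.2 |
| 0.5 | 0.9 | 1.3 | 0.5 |
| 0.8 | 1.8 | 4.2 | 2.5 |

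The largest gain is from 72.5% to 76.7%. Gains of a few tenths of a point are within simulation noise.

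**5. Risk difference (side point).** Crude SE = √(0.40×0.60/128 + 0.20×0.80/192) = √0.002708 = 0.05204, so the 95% half-width is 1.96×0.05204 = 10.20 points. With 60:40 allocation in both strata, the Mantel-Haenszel weights equal the stratum shares, and SE² = Σ wₖ²[pₖ(1−pₖ)/(128wₖ) + qₖ(1−qₖ)/(192wₖ)]. The assumptions are 5–30% under 18, an age gap in placebo failure of 0–30 points, and active failure at half of placebo in each stratum. The most favourable case is 30% under 18 with placebo failure 19% in adolescents and 49% in adults. It gives SE 0.05036 and half-width 9.87 points, a variance 6.4% smaller. At 10% under 18 and a 20-point gap the half-width is 10.14; with no gap it stays at 10.20.

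**The case against.** The strongest reply is that nothing decisive turns on this. The plain Wilcoxon test does not inflate the error rate, the only formal decision rule (SAP 5.2) serves the primary hypothesis, and the primary CMH test is already stratified. All of that stands, and it sets the priority.

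The size is also conditional. The simulation uses all 320 patients, but SAP 9.3 says the BSS came in with Amendment 3, and SAP 7.1 refers to patients treated under Amendments 1 and 2. The BSS comparison therefore has fewer patients, and the absolute power figures above do not carry over directly. SAP 9.3 also leaves unclear whether the Wilcoxon sentence governs ordinal endpoints other than the BSS, such as nausea severity.

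It could be said that 7.3 speaks of secondary endpoints, whereas SAP 7.1 and 9.3 group secondary and tertiary together. That does not exempt the BSS, which the protocol and SAP 3.2 both list as secondary.

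Two stronger readings are tempting and do not hold:

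- A reader might infer that the SAP declares the risk difference unstratified. It does not. SAP 9.2 says "The point estimate of the difference of the proportions between treatment arms will also be provided along with corresponding 2-sided 95% confidence intervals" and names no method. The same section also reports a common odds ratio with its interval, so the age-stratified test already has a matching estimate.
- A reader might infer that the tests within baseline nausea-severity groups must also be stratified, since SAP 9.2 says "For a given severity group, unstratified CMH test will be performed" and age still varies within those groups. This is an explicit choice for supportive analyses of the primary endpoint. In simulated subgroups of 50, 107 and 160 patients (6,000 runs; assumed 10–30% under 18 and a 10–30 point age gap), stratifying changed power by −1.2 to +2.5 points, with the losses in the smaller groups. That is a trade-off, not a defect.

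**Conclusion.** The inconsistency between SAP 7.3 and 9.3 item 4 is certain from the text. Its consequence is small and depends on facts the documents do not give. With an assumed 10–30% of patients under 18, naming the stratum gains about 0 to 1 point of power for age shifts up to 0.5 SD and about 2 to 4 points at 0.8 SD. If age is not prognostic, the gain is nil. It would go too far to say that the plan wastes precision: the documents do not show that age predicts stool outcome. The Wilcoxon result would be valid, at worst slightly conservative, and the primary p-value does not change. This is a minor point, worth correcting because the correction costs almost nothing.

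**What to change.** In SAP 9.3 item 4, name the van Elteren test (Wilcoxon rank sum stratified by age, <18 and ≥18) for the BSS, and say that it applies to any other ordinal secondary endpoint, in line with 7.3. The Supplemental SAP records that the study was unblinded on June 3, 2017. The stratified result should therefore be reported beside the Wilcoxon test as written rather than in its place, with the disagreement between the two sections disclosed in the study report.

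Optionally, state in 9.2 how the risk difference and its interval are calculated, for example with Mantel-Haenszel weights by age. No change to the severity-group tests is asked for.

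The cost is a sentence or two of text and one extra run of a standard procedure on data already collected.

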9.4. Safety Analyses

The safety and tolerability of RHB-102 will be determined by reported AEs, physical examinations, vital signs, and, if performed on study, laboratory tests. Subjects who receive any RHB-102 (even if they vomit shortly after administration) are considered evaluable for safety. Physical exam findings will not be analyzed separately. Rather, new and worsening abnormalities will be considered AEs and analyzed with those data.

1) Adverse Events

The NCI-CTCAE v4.0 system will be used to grade new or worsening laboratory abnormalities. New laboratory abnormalities for which there are no CTCAE v4.0 criteria will be assigned grade 1 if there were no clinical effects or interventions, and according to the criteria in protocol section 6.3 if there were clinical effects and/or interventions. AEs will be grouped and tabulated by MedDRA preferred terms by system organ class.

The Medical Dictionary for Regulated Activities (MedDRA) version 13.1 will be used to classify all AEs with respect to system organ class and preferred term.

Summary tables of AEs and SAEs will be prepared by system organ class, preferred term and severity for each treatment group. AEs that lead to premature discontinuation from the study or to death will be listed separately via data listings.

2) Other Parameters

Findings on physical examination, including vital signs, which constitute clinically significant changes, will be listed as adverse events. The incidence of hospitalization will be compared between treatment groups as an efficacy parameter. The causes for hospitalization, other than for gastroenteritis, will be listed as SAEs.

ECGs of patients who undergo paired ECGs on the study will be analyzed for shifts in QTcF and QTcB.

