#### 4.4.2 Serotonin syndrome

5-HT3 antagonists, including ondansetron, have been associated with serotonin syndrome. When given as a single agent, ondansetron overdose has been associated with serotonin syndrome. However, most reports of serotonin syndrome have been associated with concomitant use of serotonergic drugs (e.g., selective serotonin reuptake inhibitors (SSRIs), serotonin and norepinephrine reuptake inhibitors (SNRIs), monoamine oxidase inhibitors, mirtazapine, fentanyl, lithium, tramadol, and intravenous methylene blue). Some of the reported cases were fatal.

Symptoms associated with serotonin syndrome may include the following combination of signs and symptoms: mental status changes (e.g., agitation, hallucinations, delirium, and coma), autonomic instability (e.g., tachycardia, labile blood pressure, dizziness, diaphoresis, flushing, hyperthermia), neuromuscular symptoms (e.g., tremor, rigidity, myoclonus, hyperreflexia, incoordination), seizures, with or without gastrointestinal symptoms (e.g., nausea, vomiting, diarrhea). Patients should be warned about and monitored for the emergence of serotonin syndrome, especially with concomitant use of other serotonergic drugs. If symptoms of serotonin syndrome occur, discontinue RHB-102 and initiate supportive treatment.

All medications taken in the 7 days prior to study entry and from the time the patient arrives in the emergency room until he or she completes the study will be recorded in the case report form (CRF).

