#### 4.6 Discontinuation of Treatment

Patients may take study medication daily for up to 4 days (day 1 medication is the one or two tablets administered in the emergency department).

- If a patient vomits or otherwise receives rescue medication in the emergency department, he or she is not to receive additional study medication, even if nausea and/or vomiting is controlled with rescue medication.
- If the QTc interval at 4 hours after initial dose of study medication is >500 msec, study medication is to be discontinued.
- Patients experiencing recurrent nausea or vomiting after discharge from the emergency department and initial discontinuation of study medication due to resolution of symptoms may opt to resume study medication.

If a patient experiences an adverse event, regardless of relationship to study medication, which, in the investigator's opinion endangers or makes it difficult to evaluate the patient, the investigator may elect to have the patient stop study medication.

If once on study, a patient requires a medication which may prolong the QTc interval, he or she should not receive further study medication. However, evaluation of the patient should continue per protocol.

Patients may elect to discontinue treatment at any time.

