#### 5.2.3 Procedures after discharge from emergency department:

Any patient who has a post-dosing ECG showing QTc>500 msec must have a follow-up ECG within 72 hours of initial dosing showing resolution of the QTc prolongation. This may be performed on an inpatient or outpatient basis at the investigator's discretion. If the QTc does not decrease below 500 msec during initial follow-up, the medical monitor must be contacted to discuss further follow-up.

If a patient vomits from 30 minutes after taking the first dose of study medication until 24 hours after the first dose of study medication or requires rescue antiemetic or parenteral hydration during that period, even without vomiting, he or she will be considered a treatment failure. In that case, the only post-emergency department follow-up will be a call 72-96 hours after discharge from the emergency department to ascertain whether the patient's symptoms have

resolved, whether any adverse events occurred, and whether the patient required further medical follow-up, either in an emergency department or other medical facility.

Prior to discharge, patients who are treatment successes (i.e., no vomiting, no rescue medication and no parenteral hydration while in emergency department) will be given a diary card to record:

- all episodes of vomiting and bowel movements, with description of each bowel movement
- severity of nausea (on a 5-point Likert scale) three times a day: before breakfast or the time at which the patient usually eats breakfast, between 1:00-2:00 pm, and at bedtime
- any symptoms the patient may have related to gastroenteritis, such as chills, fever, abdominal pain
- adverse events
- medications taken, either for gastroenteritis (study medication and others) or other conditions

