## 6. Safety Reporting

All subjects will be assessed regularly for potential adverse events (AEs) occurring at any time after the subject signs the informed consent, until discharge after the last dose of study medication. AEs ongoing at the time of last dose of study medication will be followed until resolution or until 30 days after the last dose of study medication, whichever comes first. Post-study follow-up will be by telephone or e-mail after subjects are discharged. All subjects dosed will be contacted per the schedule above and queried regarding the occurrence of AEs and serious adverse events (SAEs).

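### The only listing of discontinuation AEs is keyed to leaving the study, but the protocol's safety stops end study medication, so those stops would not be identified

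*SAP*

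**What the plan says.** SAP 9.4, under Adverse Events, plans two kinds of AE output. The first is tabular: "Summary tables of AEs and SAEs will be prepared by system organ class, preferred term and severity for each treatment group". The second is a listing: "AEs that lead to premature discontinuation from the study or to death will be listed separately via data listings". Protocol 7.5.1 plans the same outputs in the same words. SAP 9.4 also analyses paired ECGs for shifts in QTcF and QTcB.

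The protocol's safety rules are worded in terms of study medication:

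- Section 4.6, ECG rule: "If the QTc interval at 4 hours after initial dose of study medication is >500 msec, study medication is to be discontinued".
- Section 4.6, AE that endangers the patient or hampers evaluation: "the investigator may elect to have the patient stop study medication".
- Section 4.4.2: "If symptoms of serotonin syndrome occur, discontinue RHB-102 and initiate supportive treatment".
- Sections 4.4 and 4.6, patient needs a drug that may prolong QTc: "he or she should not receive further study medication. However, evaluation of the patient should continue per protocol".

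On what follows a stop, protocol 5.2.3 says that a patient with a post-dosing QTc above 500 msec "must have a follow-up ECG within 72 hours of initial dosing showing resolution of the QTc prolongation". Protocol section 6 adds, for any patient, "AEs ongoing at the time of last dose of study medication will be followed until resolution or until 30 days after the last dose".

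**The concern.** The listing asks whether an AE took the patient out of the study. The protocol's safety rules ask whether the patient should go on taking the tablets. These are different events, and the protocol keeps them apart. A patient can be taken off study medication after the first dose for a safety reason, complete follow-up as intended, and never meet the listing criterion.

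The distinction matters in this design. The protocol excludes patients with QTc above 450 msec (3.2), requires a repeat ECG at 4 hours (4.1) and sets a stop above 500 msec (4.6). Up to three take-home doses can follow the emergency department dose (4.5), so a stop after the first dose withholds treatment that the patient could otherwise have used. A reader of the report would expect to learn how many patients in each arm were stopped for safety, and why. An empty listing could be taken to mean that none were, when the criterion never asked.

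**Working it through.** No arithmetic applies, and the plan states no figure to reproduce. The check sets the listing criterion (the AE led to leaving the study, or to death) beside each stop rule.

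| Stop rule | Protocol section | What ends | What is said about follow-up | Listed if the patient stays in follow-up and survives? |
|---|---|---|---|---|
| QTc above 500 msec at 4 hours | 4.6 | Study medication | Follow-up ECG required (5.2.3) | No |
| AE, investigator's election | 4.6 | Study medication | Nothing specific to the stop; general AE follow-up (6) | No |
| Serotonin syndrome symptoms | 4.4.2 | RHB-102 | Nothing specific to the stop; general AE follow-up (6) | No |
| Need for a QTc-prolonging drug | 4.4, 4.6 | Study medication | Evaluation expressly continues | No; also not in itself an AE |

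**Could leaving the study be read to include stopping the tablets?** Neither document defines it so. Both treat leaving as its own status: patients who drop out of the study are imputed as failures (protocol 7.4.3, SAP 8 and 9.2), and the supplemental SAP gives early dropout a separate code (section 11). The rule on QTc-prolonging drugs separates the two explicitly, ending medication while evaluation goes on.

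**Does another output identify these stops?** The AE tables are by organ class, term and severity, with no breakdown by what happened to study medication. The ECG analysis shows QTc values but not that dosing stopped. The sections of the supplemental SAP available here add listings of redosed patients and of exclusions from Subgroup Population 1 (15, 16), but none of safety stops.

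**Which stops belong to the point?** The first three rows are driven by an AE or by an ECG finding that may be recorded as one, since protocol 6.6 sends clinically significant ECG changes to the AE page. The fourth is triggered by a concomitant drug. An AE listing would capture it only if the underlying reason had been recorded as an AE, so it needs separate treatment.

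**The case against.** The strongest reply is that nothing disappears. Clinically significant ECG changes go on the AE page, every AE is tabulated by arm and severity, and QTc is analysed for shifts. That stands, and it limits the point. A reader might infer that the trial's QTc risk would be understated. The documents do not support that, because both the QTc values and the AEs are reported; only the link to the medication stop is missing.

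A reader might also want a number of patients missing from the listing. None can be given. The documents state no rate of safety stops, and SAP 9.1 says that paired ECGs were required of all patients only from amendment 4 (March 2016). The whole arm of 192 is therefore not a sound denominator for stops under the QTc rule.

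Two further objections stand in part. For the investigator-elected and serotonin syndrome stops, the protocol does not say whether the patient stays in the study. The claim is therefore that these rules do not require leaving, not that no such patient leaves; one who also withdrew because of the AE would be listed. Second, simply adding discontinuation of study medication would be too loose here. Take-home dosing is as needed, patients may stop when symptoms resolve and later resume, and vomiting or rescue in the emergency department also ends dosing (4.5, 4.6). The criterion must be tied to a safety reason.

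**Conclusion.** The mismatch is real and minor. By its wording, the listing in SAP 9.4 and protocol 7.5.1 omits any surviving patient whose study medication was stopped under an AE-driven rule and who remained in follow-up. No other output in the material available identifies such patients. What is lost is the identification, by arm and reason, of events that ended study medication.

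The conclusion rests on the ordinary meaning of leaving the study and on the absence of any broader definition. It does not depend on any assumed event rate. The primary efficacy analysis, the AE tables and the QTc shift analysis are unaffected.

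**What to change.** In SAP 9.4 and protocol 7.5.1, change the criterion to AEs leading to discontinuation of study medication, to discontinuation from the study, or to death, and keep the three outcomes distinguishable. Alongside the listing, give the count by arm with the reason for each stop.

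- Name stops under the QTc above 500 msec rule as included, so that they do not depend on whether the ECG finding was entered as an AE.
- Show stops for need of a QTc-prolonging drug separately, because they are not AEs in themselves.
- Exclude stops due to symptom resolution or treatment failure.

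This changes reporting only and leaves every clinical rule as it is.

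The supplemental SAP (section 3) records unblinding on June 3, 2017. If the output is produced for this trial's report, it should be labelled a post-unblinding addition. SAP 3 already sends departures from the plan to the Clinical Study Report, and the supplemental SAP has added patient listings after unblinding.

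The cost is a phrase in two places and one small table. Dosing, ECG and AE data are collected, but neither document shows a dedicated field for action taken with study medication, so attributing a stop to an AE may need case-by-case review of those records.
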